# 9.5. Interim Analyses

An interim analysis will be conducted on accrued data through Day 183 for publication purposes.

The SAP will describe the planned interim analyses in greater detail.

# 9.6. Data Monitoring Committee

This study will not include a Data Monitoring Committee (DMC).

# 10. SUPPORTING DOCUMENTATION AND OPERATIONAL CONSIDERATIONS

# 10.1. Appendix 1: Regulatory, Ethical, and Study Oversight Considerations

### 10.1.1. Regulatory and Ethical Considerations

- This study will be conducted in accordance with the protocol and with the following:
  - Consensus ethical principles derived from international guidelines including the Declaration of Helsinki and Council for International Organizations of Medical Sciences (CIOMS) International Ethical Guidelines
  - Applicable ICH GCP Guidelines
  - Applicable laws and regulations
- The protocol, protocol amendments, ICF, IB, and other relevant documents (eg, advertisements) must be submitted to an IRB/IEC by the Investigator and reviewed and approved by the IRB/IEC before the study is initiated.
- Any amendments to the protocol will require IRB/IEC approval before implementation of changes made to the study design, except for changes necessary to eliminate an immediate hazard to study participants.
- The Investigator will be responsible for the following:
  - Providing written summaries of the status of the study to the IRB/IEC annually or more frequently in accordance with the requirements, policies, and procedures established by the IRB/IEC
  - Notifying the IRB/IEC of SAEs or other significant safety findings as required by IRB/IEC procedures
  - Providing oversight of the conduct of the study at the site and adherence to requirements of 21 CFR, ICH guidelines, the IRB/IEC, European regulation 536/2014 for clinical studies (if applicable), and all other applicable local regulations

## 10.1.2. Financial Disclosure

Investigators and sub-investigators will provide Alexion with sufficient, accurate financial information as requested to allow Alexion to submit complete and accurate financial certification or disclosure statements to the appropriate regulatory authorities. Investigators are responsible for providing information on financial interests during the course of the study and for 1 year after completion of the study.

#### **10.1.3.** Informed Consent Process

- The Investigator or his/her representative will explain the nature of the study to the participant or his/her legally authorized representative and answer all questions regarding the study.
- Participants must be informed that their participation is voluntary. Participants or their legally authorized representative, defined according to local and country regulations where the study is taking place, will be required to sign a statement of informed consent that meets the requirements of 21 CFR 50, local regulations, ICH guidelines, Health Insurance Portability and Accountability Act requirements, where applicable, and the IRB/IEC or study center.
- The medical record must include a statement that written informed consent was obtained before the participant was screened in the study and the date the written consent was obtained. The authorized person obtaining the informed consent must also sign the ICF(s).
- Participants must be re-consented to the most current version of the ICF(s) during their participation in the study.
- A copy of the ICF(s) must be provided to the participant or the participant's legally authorized representative.

#### **10.1.4.** Data Protection

- Participants will be assigned a unique identifier by Alexion. Any participant records or datasets that are transferred to Alexion will contain the identifier only; participant names or any information which would make the participant identifiable will not be transferred.
- The participant must be informed that his/her personal study-related data will be used by Alexion in accordance with local data protection law. The level of disclosure must also be explained to the participant who will be required to give consent for their data to be used as described in the informed consent.
- The participant must be informed that his/her medical records may be examined by Clinical Quality Assurance auditors or other authorized personnel appointed by Alexion, by appropriate IRB/IEC members, and by inspectors from regulatory authorities.

### 10.1.5. Dissemination of Clinical Study Data

Study-related information and study results may be posted on publicly accessible clinical study databases (eg, the US website www.clinicaltrials.gov or the EU website www.clinicaltrialsregister.eu), as appropriate, and in accordance with national, regional, and local regulations.

### 10.1.6. Data Quality Assurance

• All participant data relating to the study will be recorded on a printed or eCRF unless transmitted to Alexion or designee electronically (eg, laboratory data). The

investigator is responsible for verifying that data entries are accurate and correct by physically or electronically signing the CRF.

- The Investigator must maintain accurate documentation (source data) that supports the information entered in the eCRF.
- The Investigator must permit study-related monitoring, audits, IRB/IEC review, and regulatory agency inspections and provide direct access to source data documents.
- Alexion or designee is responsible for the data management of this study including quality checking of the data.
- Study monitors will perform ongoing source data verification to confirm that data entered into the eCRF by authorized site personnel are accurate, complete, and verifiable from source documents; that the safety and rights of participants are being protected; and that the study is being conducted in accordance with the currently approved protocol and any other study agreements, ICH GCP, and all applicable regulatory requirements.
- Records and documents, including signed ICFs, pertaining to the conduct of this study must be retained by the Investigator for 2 years after the last marketing application approval, or if not approved, 2 years following the discontinuance of the test article for investigation, unless local regulations or institutional policies require a longer retention period. No records may be destroyed during the retention period without the written approval of Alexion. No records may be transferred to another location or party without written notification to Alexion.

## **10.1.7.** Source Documents

- Source documents provide evidence for the existence of the participant and substantiate the integrity of the data collected. The Investigator or designee will prepare and maintain adequate and accurate source documents (eg, medical records, ECGs, AE and concomitant medication reporting, raw data collection forms) designed to record all observations and other pertinent data for each participant.
- Data entered in the eCRF that are transcribed from source documents must be consistent with the source documents or the discrepancies must be explained. The Investigator may need to request previous medical records or transfer records, depending on the study. Also, current medical records must be available. Source documents are filed at the Investigator's site.

## 10.1.8. Study and Site Start and Closure

The study start date is the date on which the clinical study will be open for recruitment of participants.

The first act of recruitment is the first site open and will be the study start date.

Alexion or designee reserves the right to close the study site or terminate the study at any time for any reason at the sole discretion of Alexion. Study sites will be closed upon study

completion. A study site is considered closed when all required documents and study supplies have been collected and a study-site closure visit has been performed.

The Investigator may initiate study-site closure at any time, provided there is reasonable cause and sufficient notice is given in advance of the intended termination.

Reasons for the early closure of a study site by Alexion or Investigator may include but are not limited to:

- Failure of the Investigator to comply with the protocol, the requirements of the IRB/IEC or local health authorities, Alexion-s procedures, or GCP guidelines
- Inadequate recruitment of participants by the Investigator
- Discontinuation of further study drug development

If the study is prematurely terminated or suspended, Alexion shall promptly inform the Investigators, the IECs/IRBs, the regulatory authorities, and any contract research organization(s) used in the study of the reason for termination or suspension, as specified by the applicable regulatory requirements. The Investigator shall promptly inform the participant and should assure appropriate therapy and/or follow-up.

## **10.1.9. Publication Policy**

The full terms regarding publication of the results of this study are outlined in the applicable Clinical Study Agreement.

# **10.2.** Appendix 2: Clinical Laboratory Tests

- The tests detailed in Table 6 will be performed by both the central laboratory and the local laboratory.
- Local laboratory results are only required in the event that the central laboratory results are not available in time for either study drug administration and/or response evaluation. If a local sample is required, it is important that the sample for central analysis is obtained at the same time. Additionally, if the local laboratory results are used to make either a study drug decision or response evaluation, the results must be entered into the eCRF.
- Protocol-specific requirements for inclusion or exclusion of participants are detailed in Section 5 of the protocol.
- Additional tests may be performed at any time during the study as determined necessary by the Investigator or required by local regulations.
- Pregnancy Testing (see Section 10.4.3)

Hematology	Clinical Chemistry
Free hemoglobin	Alanine aminotransferase
Haptoglobin	Albumin
Hematocrit	Alkaline phosphatase
Hemoglobin	Aspartate aminotransferase
Mean corpuscular hemoglobin	Bicarbonate
Platelet count	Blood urea nitrogen
RBC count	Calcium
RBC distribution width	Chloride
RBC mean corpuscular volume	C-reactive protein
Reticulocyte count	Creatinine
WBC count	Gamma-glutamyltransferase
WBC differential	Glucose
	Lactate dehydrogenase
Coagulation Panel	Magnesium
	Phosphorus
D-dimer	Potassium
International normalized ratio	Sodium
Partial thromboplastin time	Total bilirubin (direct and indirect)
Prothrombin time	Total protein
	Uric acid
Urinalysis	
Albumin	Virus Serology
Appearance	
Bilirubin	HIV-1
Blood	111 V -2
Color	
Creatinine	Other
Glucose	Antidrug antibody
Ketone	Beta human chorionic gonadotropin (women of
Nitrite	childbearing potential only)
pH	Free and total C5
Protein	Pharmacokinetic assay
Specific gravity	PNH clone size
Urobilinogen	Serum follicle-stimulating hormone (postmenopausal
-	females only)

## Table 6: Protocol-Required Safety Laboratory Assessments

Investigators must document their review of each laboratory safety report.

# 10.3. Appendix 3: Adverse Events: Definitions and Procedures for Recording, Evaluating, Follow-up, and Reporting

#### **Adverse Event Definition**

- An AE is any untoward medical occurrence in a participant or clinical study participant, temporally associated with the use of study drug, whether or not considered related to the study drug.
- NOTE: An AE can therefore be any unfavorable and unintended sign (including an abnormal laboratory finding), symptom, or disease (new or exacerbated) temporally associated with the use of study drug.

#### **Events** Meeting the AE Definition

- Any abnormal laboratory test results (hematology, clinical chemistry, or urinalysis) or other safety assessments (eg, ECG, radiological scans, vital signs measurements), including those that worsen from baseline, considered clinically significant in the medical and scientific judgment of the Investigator (ie, not related to progression of underlying disease).
- Exacerbation of a chronic or intermittent pre-existing condition including either an increase in frequency and/or intensity of the condition.
- New conditions detected or diagnosed after study drug administration even though it may have been present before the start of the study.
- Signs, symptoms, or clinical sequelae whether or not related to a suspected drug-drug interaction.
- "Lack of efficacy" or "failure of expected pharmacological action" per se will not be reported as an AE or SAE. Such instances will be captured in the efficacy assessments. However, the signs, symptoms, and/or clinical sequelae resulting from lack of efficacy will be reported as AE or SAE if they fulfil the definition of an AE or SAE.

#### Events **NOT** Meeting the AE Definition

- Any clinically significant abnormal laboratory findings or other abnormal safety assessments which are associated with the underlying disease, unless judged by the Investigator to be more severe than expected for the participant's condition.
- Medical or surgical procedure (eg, endoscopy, appendectomy): the condition that leads to the procedure is the AE.
- Situations in which an untoward medical occurrence did not occur (social and/or convenience admission to a hospital).
- Anticipated day-to-day fluctuations of pre-existing disease(s) or condition(s) present or detected at the start of the study that do not worsen.

# **Serious Adverse Event Definition**

If an event is not an AE per definition above, then it cannot be an SAE even if serious conditions are met (eg, hospitalization for signs/symptoms of the disease under study, death due to progression of disease).

#### An SAE is defined as an AE that, at any dose:

#### 1. Results in death

#### 2. Is life-threatening

The term 'life-threatening' in the definition of 'serious' refers to an event in which the participant was at risk of death at the time of the event. It does not refer to an event, which hypothetically might have caused death, if it were more severe.

#### 3. Requires inpatient hospitalization or prolongation of existing hospitalization

#### An SAE is defined as an AE that, at any dose:

In general, hospitalization signifies that the participant has been detained (usually involving at least an overnight stay) at the hospital or emergency ward for observation and/or treatment that would not have been appropriate in the physician's office or outpatient setting. Complications that occur during hospitalization are AEs. If a complication prolongs hospitalization or fulfills any other serious criteria, the event is serious. When in doubt as to whether "hospitalization" occurred or was necessary, the AE should be considered serious.

Hospitalization for elective treatment of a pre-existing condition that did not worsen from baseline is not considered an AE.

- 4. Results in persistent disability/incapacity
- The term disability means a substantial disruption of a person's ability to conduct normal life functions.
- This definition is not intended to include experiences of relatively minor medical significance such as uncomplicated headache, nausea, vomiting, diarrhea, influenza, and accidental trauma (eg, sprained ankle) which may interfere with or prevent everyday life functions but do not constitute a substantial disruption.

#### 5. Is a congenital anomaly/birth defect

#### 6. Other situations:

- Medical or scientific judgment should be exercised in deciding whether SAE reporting is appropriate in other situations such as important medical events that may not be immediately life-threatening or result in death or hospitalization but may jeopardize the participant or may require medical or surgical drug to prevent one of the other outcomes listed in the above definition. These events should usually be considered serious.
- Examples of such events include invasive or malignant cancers, intensive treatment in an emergency room or at home for allergic bronchospasm, blood dyscrasias or convulsions that do not result in hospitalization, or development of drug dependency or drug abuse.

# Recording and Follow-Up of Adverse Event and/or Serious Adverse Event

#### Adverse Event and Serious Adverse Event Recording

- When an AE/SAE occurs, it is the responsibility of the Investigator to review all documentation (eg, hospital progress notes, laboratory reports, and diagnostics reports) related to the event.
- The Investigator will then record all relevant AE or SAE information in the eCRF.
- It is not acceptable for the Investigator to send photocopies of the participant's medical records to Alexion in lieu of completion of the AE/SAE eCRF page.
- There may be instances when copies of medical records for certain cases are requested by Alexion. In this case, all participant identifiers, with the exception of the participant number, will be redacted on the copies of the medical records before submission to Alexion.
- The Investigator will attempt to establish a diagnosis of the event based on signs, symptoms, and/or other clinical information. Whenever possible, the diagnosis (not the individual signs/symptoms) will be documented as the AE/SAE.

#### Assessment of Intensity

The Investigator will make an assessment of intensity for each AE and SAE reported during the study and assign it to 1 of the following categories from National Cancer Institute CTCAE v5.0, published 27 Nov 2017:

- Grade 1: Mild (awareness of sign or symptom, but easily tolerated)
- Grade 2: Moderate (discomfort sufficient to cause interference with normal activities)
- Grade 3: Severe (incapacitating, with inability to perform normal activities)
- Grade 4: Life-threatening
- Grade 5: Fatal

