11.1. Adverse Events

Adverse events will be summarized by SOC and PT for the Safety Set. TEAEs are defined as AEs which commence on or after the first administration of the study drug, or those that occur before first study drug administration but worsen in frequency or severity after first study drug administration. All other AEs are considered PTAE.

TEAEs and PTAEs will be included in the summary tables; separate listings for TEAEs and PTAEs will be produced. Additional listings will be provided for deaths, SAEs, TEAEs leading to study drug withdrawal, TEAEs considered MAVE, and TEAEs of special interest.

Meningococcal infections will be collected as TEAEs of special interest. In addition, a medical review will be done to ensure that no relevant events were missed.

If the relationship to study drug is missing for TEAEs, then the relationship will be counted as related to study product for the summary tables. Missing severity for TEAEs will be counted as Grade 3.

Tables will be sorted by descending frequency of SOC and by descending frequency of PT within SOC, based on MedDRA version 23.1. Participants having multiple AEs within a category (eg, overall, SOC, PT) will be counted once in that category. For severity/relationship tables, the participant's highest grade/most related event within a category will be counted. Percentages will be based on the number of participants in the Safety Set.

An overall summary table of TEAEs will be presented using summary statistics (n, %). The number of events (n) and number of participants with events (n, %) will be displayed for the following events subcategories:

The following tables will be provided:

- An overall summary of the number and percentage of participants reporting TEAEs, treatmentemergent SAEs (TESAEs), TEAEs leading to death, TEAEs leading to withdrawal of study drug, TEAEs by maximum relationship, TESAEs by maximum relationship, TEAEs by maximum Common Terminology Criteria for Adverse Events (CTCAE) grade, TEAEs considered MAVE, TEAEs of special interest, and TEAEs related to COVID-19 infection
- PTAEs overall and by SOC and PT;
- TEAEs overall and by SOC and PT;
- TEAEs by maximum CTCAE grade, overall and by SOC and PT;
- TEAEs related to study drug, overall and by SOC and PT;
- TESAEs overall and by SOC and PT;
- TESAE related to study drug, overall and by SOC and PT;
- TEAEs considered MAVE, overall and by SOC and PT.

This document is confidential.

SAP Version: 2.0 09-Feb-2023

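### SAP 11.1 counts every TEAE with missing severity as Grade 3, so an ungraded fatal or life-threatening event is tabulated below the protocol's own grade for it

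*Protocol*

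**What the plan says.** **Grading (Protocol Section 10.3, Appendix 3, Assessment of Intensity).** A grade is required for every event: "The Investigator will make an assessment of intensity for each AE and SAE reported during the study". The investigator is to "assign it to 1 of the following categories from National Cancer Institute CTCAE v5.0, published 27 Nov 2017". The scale has five printed levels:

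- The lowest is worded by awareness: "Grade 1: Mild (awareness of sign or symptom, but easily tolerated"
- The second is worded by its effect on daily life: "Grade 2: Moderate (discomfort sufficient to cause interference with normal activities"
- The third is worded by loss of function: "Grade 3: Severe (incapacitating, with inability to perform normal activities"
- The fourth is an outcome and not a symptom level: "Grade 4: Life-threatening"
- The highest, Grade 5, is likewise an outcome: a fatal event.

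**What can be an adverse event (Section 10.3).** Laboratory abnormalities are included: "Any abnormal laboratory test results (hematology, clinical chemistry, or urinalysis" and other safety assessments count when the investigator judges them clinically significant. The general AE definition in the same appendix treats an abnormal laboratory finding as a kind of sign.

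**Analysis (SAP Section 11.1).** "Missing severity for TEAEs will be counted as Grade 3". A missing relationship is counted as related. Each participant is counted at the highest grade within a category. The overall summary reports TEAEs leading to death and also TEAEs by maximum CTCAE grade. A further table gives maximum grade by SOC and PT, and deaths have a separate listing.

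**The concern.** A rule for missing severity is normally meant to be cautious. The companion rule for relationship is: a blank is given the worst value. Grade 3 is a cautious value for most events, but not for one already known to be fatal or life-threatening, because the protocol's scale fixes those at Grades 5 and 4. For such events the default lowers the grade, and it replaces something that can be derived with something assumed.

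At stake is the internal consistency of the severity tables. The overall summary could show a death-related TEAE beside an empty Grade 5 row. The SAP runs all its outputs at the interim, which is intended for publication, so the inconsistency could be published.

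A separate and smaller question is what the grade means for laboratory events. The printed Grades 2 and 3 turn on discomfort and inability to perform normal activities. The scale is attributed to CTCAE v5.0 and the SAP labels its output as CTCAE grade, but neither document says whether the printed descriptors or term-specific criteria decide the grade.

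**Working it through.** The plan states no figure on this point, so there is none to reproduce. The check sets the texts side by side and then does simple arithmetic for scale.

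**1. The default against the scale**

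| Event, severity left blank | Grade by the protocol's scale | Grade under SAP 11.1 | Difference |
|---|---|---|---|
| Fatal TEAE | 5 | 3 | 5 − 3 = 2 grades too low |
| Life-threatening, non-fatal TEAE | 4 | 3 | 4 − 3 = 1 grade too low |
| Any other TEAE | not known | 3 | cannot be judged |

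The rule covers TEAEs only; SAP 11.1 sets no grade for pre-treatment events.

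**2. What the overall summary would show**

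Inputs: approximately 20 participants (Protocol 9.2, SAP 3.3); the first 10 participants at the interim (SAP 13). Assume one fatal TEAE with a blank grade and no other Grade 5 event. Assume also that the death row is built from the recorded outcome and not from the grade; the SAP does not spell out the derivation.

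- Final analysis: leading to death 1/20 = 5.0%; Grade 5 0/20.
- Interim: leading to death 1/10 = 10.0%; Grade 5 0/10.

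The empty row would be visible, because SAP 16.2.5.2 displays every category even when its count is zero.

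**3. How far the grade rows can move**

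One participant is 1/20 = 5.0 percentage points of a row, or 1/10 = 10.0 points at the interim. A row moves only if the imputed event decides that participant's highest grade. Moving an event from Grade 5 to Grade 3 leaves the combined count at Grade 3 or above unchanged. The error is in how severe events are split among the top three grades.

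**4. The laboratory question**

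Take a laboratory AE that causes no symptoms and is neither life-threatening nor fatal.

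- Grade 1 refers to awareness of a sign or symptom. The AE definition counts an abnormal laboratory finding as a sign, so Grade 1 can apply.
- Grade 2 requires discomfort that interferes with normal activities, and Grade 3 requires incapacity. Neither fits readily, however marked the abnormality.
- An investigator who relies on the printed words and one who consults the named source could therefore grade differently, and both results would enter one table labelled as CTCAE grade. Whether they would differ in practice cannot be checked, because the CTCAE text is not in the documents.
- SAP 11.2 does not fill the gap with a severity grade: its shift tables use low, normal and high only.

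**The case against.** The best case for the plan is that the fatal example is remote. Intensity is mandatory for each event, study monitors verify that eCRF entries are complete (Protocol 10.1.6), and SAEs are reported within 24 hours and followed up. A fatal event would have to stay ungraded through to the analysis. Even then it would appear among TEAEs leading to death and in the deaths listing, and the mismatch would be easy to see. All of this stands, and it limits the point to the grade tables. It does not rescue the rule: the SAP provides for blanks, and for fatal and life-threatening events the value it assigns contradicts the scale.

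A reader might go further and infer that laboratory AEs have no usable grade, or that investigators will leave them blank and so push them into Grade 3. The documents do not support either inference. A laboratory finding counts as a sign, so Grade 1 is available; Grades 4 and 5 rest on outcome and can apply; CTCAE v5.0 is the named source; and leaving the grade blank is not an option the protocol offers.

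Nor do the documents show that laboratory AEs will be common. Section 10.3 excludes findings associated with the underlying disease unless they are more severe than expected, and asks for the diagnosis in place of individual signs where possible. Laboratory safety is also analysed without grades in SAP 11.2, through by-visit summaries, shift tables, plots and listings.

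**Conclusion.** The point holds, and it is narrow. The missing-severity rule in SAP 11.1 gives a grade known to be wrong for an ungraded fatal TEAE (two grades low) or an ungraded life-threatening one (one grade low). One fatal case would produce 1/20 leading to death against 0/20 at Grade 5, or 1/10 against 0/10 at the interim.

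The frequency is not known from the documents and should be low. No efficacy result or laboratory summary is affected. The separate count and listing of deaths are unaffected too, provided the death row is not derived from the grade. The Grade 4 part assumes that the life-threatening criterion, which is part of the protocol's SAE definition, is captured as a data field.

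The laboratory question is separate and lesser: an ambiguity over which criteria govern, most evident at Grades 2 and 3. It does not arise from the missing-severity rule, and that rule does not depend on it.

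**What to change.** **SAP 11.1.** Replace the single default with an ordered rule: if severity is missing for a TEAE, assign Grade 5 when the outcome is fatal; otherwise Grade 4 when the event is recorded as life-threatening; otherwise Grade 3. Footnote each grade table with the number of imputed grades, and state that the row for TEAEs leading to death is derived from outcome and not from grade.

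The cost is one or two sentences and a small derivation step. It changes no objective and nothing in study conduct, so under Protocol 9.4 it needs no protocol amendment; the change and its justification go in the CSR.

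**Protocol 10.3 or the eCRF completion guide.** State that term-specific CTCAE v5.0 criteria apply where they exist and that the printed descriptors are used for all other events. The cost is one sentence and a little more work for investigators when they grade laboratory events. If events have already been graded, a table footnote saying on which basis would keep the CTCAE label accurate.
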